8.1.1 Estimand-to-Analysis tables for secondary immunological endpoints

Table 9. Generic Estimand-to-Analysis table for all secondary Day-28 immunological endpoints (specified in Table 8).

Objectives (as per Protocol):	
Assess and compare the immune response in two randomised vaccine groups (bivalent Moderna and Novavax) at 28 days post-vaccination, measured as functional antibodies (sVNT and nAb) and cell-mediated immunity (CMI).	
Estimand:	[Measure of Association]* of [OUTCOME]* 28 days post-vaccination comparing the two vaccine groups (bivalent Moderna and Novavax) in adults 18 years or older who have received their third dose of COVID-19 vaccine at least six months previously, irrespective of SARS-CoV-2 infection.
ESTIMAND Attributes:	Incorporation of Estimand Attribute in ANALYSIS:
Treatment Bivalent mRNA Moderna COVID-19 vaccine and protein-based Novavax COVID-19 vaccine	Study arms Bivalent Moderna vaccine arm (Moderna BA.1 and Moderna BA.4-5 groups combined) Novavax vaccine arm
Target population Adults 18 years or older who have received their third dose of COVID-19 vaccine at least six months previously	Analysis set (“Secondary Day-28 Immunology Population”) All randomised participants as per randomisation with complete outcome and covariate data
Variable [OUTCOME]*, 28 days after boosting.	Outcome measure [OUTCOME]* at the Day-28 visit (25 – 35 days post-booster).
Handling of intercurrent events	
Event (up to and including Day-28 visit)	Strategy⁴
SARS-CoV-2 infection	Treatment Policy# (interpret results in conjunction with breakthrough infection rates)
Population-level summary measure Geometric mean ratio (GMR) OR Difference in Means*	
Handling of missing data The proportion of participants excluded due to missing outcome or covariate data will be described by study group.	
If >5% of participants are excluded due to missing data, a supplementary analysis will be performed with multiple imputation.	
Analysis approach Linear regression will be used to estimate the difference in mean [OUTCOME]* between the vaccine arms, adjusted for the stratifying variable (age group),	

	
first booster vaccine, time since first booster vaccine and baseline [OUTCOME]* levels.
 
Where the population-level summary measure is the GMR, the outcome variable (and the baseline value) will be \log_e transformed prior to regression, and the GMR (95% CI) will be calculated as the antilogarithms of the mean difference (β_1) and its 95% CI.
 
When zero and negative values are expected, the population-level summary measure will be the difference in medians. This will be estimated using quantile regression with the same adjustment variables as above.
 
Planned figures The distribution of the immunological data will be displayed using a scatterplot overlaid with median and interquartile range (see Dummy Figure 3)

--	---

This table is generic for all secondary Day-28 immunological endpoints (see **Table 8, which will be analysed in the same way depending on their distributions; the population measure for outcomes with skewed distributions is the geometric mean and the population-level summary measure of association is the GMR – baseline and Day-28 values will be \log_e transformed prior to analysis*

Table 10. Generic Estimand-to-Analysis table for all secondary Month-6, Month-12, Month-18 and Month-24 immunological endpoints (specified in Table 8).

Primary Objective (as per Protocol): Compare the immunogenicity in two randomised vaccine groups (bivalent Moderna and Novavax) at 6, 12, 18, 24, 30 months post-vaccination.	
Estimand:	[MoA]* of [OUTCOME]* 6/12/18/24/30 months post-vaccination comparing the two vaccine groups (bivalent Moderna and Novavax) in adults 18 years or older who have received their third dose of COVID-19 vaccine at least six months previously, irrespective of SARS-CoV-2 infection or receipt of a 5 th dose (self-initiated).
ESTIMAND Attributes:	Incorporation of Estimand Attribute in ANALYSIS:
Treatment Bivalent mRNA Moderna COVID-19 vaccine and protein-based Novavax COVID-19 vaccine	Study arms Bivalent Moderna vaccine arm Novavax vaccine arm
Target population Adults 18 years or older who have received their third dose of COVID-19 vaccine at least six months previously	Analysis set (“Month-6/12 Immunology Population”) All randomised participants as per randomisation with complete outcome and covariate data
Variable [OUTCOME]*, 6/12 months after boosting.	Outcome measure [OUTCOME]* at the Month-6/12 visit (6/12 months +/- 14 days post-booster).
Handling of intercurrent events	Handling of missing data The proportion of participants excluded due to missing outcome or covariate data will be described by study group. If >5% of participants are excluded due to missing data, a supplementary analysis will be performed with multiple imputation.
Population-level summary measure Geometric mean ratio (GMR) OR Difference in Means*	Analysis approach Linear regression will be used to estimate the difference in mean [OUTCOME]* between the vaccine arms, adjusted for the stratifying variable (age group), primary series and first booster vaccine, and baseline [OUTCOME]* levels. Where the population-level summary measure is the GMR, the outcome variable (and the baseline value) will be log_e transformed before regression, and the GMR (95% CI) will be calculated as the antilogarithms of the mean difference (β_1) and its 95% CI. When zero and negative values are expected, the population-level summary measure will be the difference in medians. This will be estimated using quantile regression with the same adjustment variables as above. The distribution of the immunological data at each timepoint will be displayed using a scatterplot

	overlaid with median and interquartile range (see Dummy Figure 3)
--	---

*This table is generic for all secondary Month-6 and Month-12 immunological endpoints (see Table 8), which will be analysed in the same way depending on their distributions; the population measure for outcomes with skewed distributions is the geometric mean and the population-level summary measure of association (MoA) is the GMR – baseline and Month-[6/12] values will be log_e transformed before analysis; the population measure for normally distributed outcomes is the mean and the population-level summary measure of association (MoA) is the Difference in Means. For outcomes with skewed distributions and negative values, the population summary measure of association is the difference in medians, which will be estimated using quantile regression.

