1.2 SCOPE OF THIS DOCUMENT

This statistical analysis plan (SAP) outlines analyses of data up to Month 30. A previous SAP (dated 19/3/2024) focused on analyses of data up to and including Day 28 visit.

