1.3 SUMMARY OF CHANGES COMPARED TO THE PROTOCOL

- The primary objective as worded in the protocol is to *“Assess and compare the immune response in two randomised vaccine groups (bivalent Moderna and Novavax) at 28 days post-vaccination measured as binding antibodies (IgG ELISA – Wuhan and/or Omicron) who have been boosted at least six months earlier.”* In this SAP, binding antibodies for Wuhan will be treated as the primary outcome, with other (sub)variants (e.g. Omicron BA.1 and Omicron BA.4/5) treated as secondary outcomes.
- The protocol specified that binding IgG data using the Euroimmun S1 IgG ELISA kits will be reported as relative units/ml (RU/ml) per the manufacturer’s instructions, with the units converted to BAU/ml for Wuhan. Whereas they will remain RU/ml for Omicron BA.1. For the Omicron BA.4/5 binding IgG data, an in-house ELISA will be used, the units are EU/ml.
- The protocol specified two different sets of adjustment variables to be included in the linear regression model for the primary analysis of the primary immunogenicity endpoint (IgG at Day-28). In this SAP, the adjustment variables have been updated to be: age group, baseline levels, first booster vaccine and time since the first booster.

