4.8 TIMING OF ANALYSES

Due to the rapidly evolving nature of the pandemic, analyses will be conducted for each immunological endpoint once the necessary data have been cleaned and locked, which will be as soon as is practicable after all participants have completed their Day-28 visit (for Day-28 endpoints), Month-6 visit (for Month-6 endpoints), Month-12 visit (for Month-12 endpoints), Month-18 (for Month-18 endpoints) and Month-24 (for Month-24 endpoint), although some of the longer-term endpoints (e.g. Month-6 and Month-12 results) may be published together. Necessary data for analysis includes those required for the reactogenicity, safety, breakthrough infection endpoints, and data on intercurrent events to the same timepoint as for the

immunological endpoint to be analysed, as these are essential for interpretation. A list of necessary variables is provided in Section 4.9.

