8 ANALYSIS OF THE SECONDARY OUTCOMES

8.1 ANALYSIS OF SECONDARY IMMUNOLOGICAL ENDPOINTS

Table 8 lists the secondary immunological endpoints, including the timepoint measured, population measure, groups being compared and the measure of association between groups. Note there may be additional secondary immunological outcome variables (e.g. relating to new variants of concern) that become available after this SAP is written. These additional variables will be analysed in the same way as other secondary immunological variables listed in Table 8, with analysis dependent on the distribution (e.g. whether symmetrical).

Table 8. Secondary immunological endpoints

Outcome	Population measure	Measure of association	Timepoint	Comparisons
Binding antibody				
Binding antibody (IgG) (Wuhan) BAU/ml	GM (95% CI)	GMR (95% CI)	Month-6	Group A vs B, Group A vs control, Group B vs control
			Month-12	Group A vs B, Group A vs control, Group B vs control
			Month-18	Group A vs B, Group A vs control, Group B vs control
			Month-24	Group A vs B, Group A vs control, Group B vs control
			Month-30	Group A vs B, Group A vs control, Group B vs control
Binding antibody (IgG) (Omicron BA.1), RU/ml	GM (95% CI)	GMR (95% CI)	Day-28	Group A vs B
			Month-6	Group A vs B, Group A vs control, Group B vs control
			Month-12	Group A vs B, Group A vs control, Group B vs control
			Month-18	Group A vs B, Group A vs control, Group B vs control
			Month-24	Group A vs B, Group A vs control, Group B vs control
			Month-30	Group A vs B, Group A vs control, Group B vs control
Binding antibody (IgG) (Omicron BA.4/5), EU/ml	GM (95% CI)	GMR (95% CI)	Day-28	Group A vs B
			Month-6	Group A vs B, Group A vs control, Group B vs control
			Month-12	Group A vs B, Group A vs control, Group B vs control
			Month-18	Group A vs B, Group A vs control, Group B vs control
			Month-24	Group A vs B, Group A vs control, Group B vs control
			Month-30	Group A vs B, Group A vs control, Group B vs control
Binding antibody (IgG) (Omicron JN.1), EU/ml	GM (95% CI)	GMR (95% CI)	Day-28	Group A vs B
			Month-6	Group A vs B, Group A vs control, Group B vs control
			Month-12	Group A vs B, Group A vs control, Group B vs control
			Month-18	Group A vs B, Group A vs control, Group B vs control
			Month-24	Group A vs B, Group A vs control, Group B vs control
			Month-30	Group A vs B, Group A vs control, Group B vs control
Functional antibody				
Functional antibody sVNT (Wuhan), U/ml	GM (95% CI)	GMR (95% CI)	Day-28	Group A vs B

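### SAP version 2.0 runs to Month 30 but gives the Month-12 outcome a ±14-day window where the protocol allows ±30, and stops its study-end SAE rows at Month 12

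*SAP*

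**What the plan says.** **Scope.** SAP 1.2 states: "This statistical analysis plan (SAP) outlines analyses of data up to Month 30".

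**Windows.** The outcome cell of SAP Table 10 places measurements "at the Month-6/12 visit (6/12 months +/- 14 days post-booster"). SAP Table 2 gives Visit 7 (12 months) ±14 days and has no columns after Visit 7. Protocol 7.1 gives Visit 6 ±14 days and Visits 7 to 10 (12, 18, 24 and 30 months) ±30 days. The section headed "SUMMARY OF CHANGES COMPARED TO THE PROTOCOL" lists three changes, none about visit windows.

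**Table 10 coverage.** The objective and estimand rows name all five later timepoints. The title reads "Generic Estimand-to-Analysis table for all secondary Month-6, Month-12, Month-18 and Month-24 immunological endpoints", so it stops at Month 24. The variable, analysis-set and outcome cells refer only to Months 6 and 12, and the footnote says "This table is generic for all secondary Month-6 and Month-12 immunological endpoints". The analysis set is "All randomised participants as per randomisation with complete outcome and covariate data", with no timing criterion. The analysis triggers in SAP 4.8 end with "Month-18 (for Month-18 endpoints) and Month-24 (for Month-24 endpoint"), while Table 8 plans Month-30 comparisons.

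**SAEs.** Table 11 rows ix and x are labelled as running to study end, but their timepoint column gives the Month-12 visit. Dummy Table S2 uses the same label with no cap. Protocol 7.1 has SAEs documented across the whole study period, and Protocol 8.2 has them followed for as long as the trial lasts. Protocol 3.2.2, SAP 6.1.2 and SAP Table 4 say 12 months. Protocol 1.3 still describes 12 months of follow-up for everyone.

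**The concern.** An outcome definition should tell two analysts which samples belong to a timepoint. Here the outcome cell leaves out Month-12 samples that the protocol permits, while the analysis set keeps them, and no sentence says which prevails. An analyst who took the cell literally would set permitted samples to missing. That could by itself push missingness past the 5% level at which Table 10 calls for a supplementary multiple-imputation analysis. For Months 18 to 30 the SAP states no window at all.

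On safety, a by-arm table that says it runs to study end but was cut at Month 12 would misstate the period over which participants were observed for SAEs. If SAEs were recorded later, they would be left out under a label that implies they are included.

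**Working it through.** No figure in the plan needs reproducing. The check compares the stated windows and timepoints and counts what is affected.

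**Month-12 window.** Inputs: ±14 days (SAP Tables 2 and 10) and ±30 days (Protocol 7.1). A window of ±w days spans 2w + 1 days.

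| Source | Half-width | Days spanned | If Month 12 is Day 365 |
|---|---|---|---|
| SAP | 14 | 2 × 14 + 1 = 29 | 351 to 379 |
| Protocol | 30 | 2 × 30 + 1 = 61 | 335 to 395 |

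Permitted by the protocol but outside the SAP definition: 61 − 29 = 32 days (335 to 350 and 380 to 395), and 32/61 = 52%. This says nothing about how many samples fall there, since visits may cluster near the target date. Month 6 is ±14 days in both documents and does not conflict.

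**Outcomes touched.** "Table 8 lists the secondary immunological endpoints, including the timepoint measured"; counting its rows for Group A versus Group B:

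- Month 12: 4 binding IgG + 3 sVNT + 2 neutralising + 2 IFN-γ = 11 outcomes under the conflicting window.
- Months 18, 24 and 30: (4 binding IgG + 3 sVNT) × 3 visits = 21 outcome-timepoints with no window in the SAP.

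**SAE horizon.** Protocol 7.2.12 puts the end of the trial at the last assay on the last sample. Once any extension sample is drawn, that date falls after Month 12, so the label and the timepoint of Table 11 rows ix and x cannot both hold. Participation can run to 30 months, so a Month-12 cut leaves 30 − 12 = 18 months, or 18/30 = 60%, outside the table. SAP 4.9 also requires adverse events to be cleaned to the timepoint of each analysis, which for Month 30 goes beyond the Month-12 cut.

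**The case against.** The strongest reply is that no rule excludes an out-of-window sample. SAP 5.3 treats a Day-28 visit outside its window as a protocol deviation, not as grounds for exclusion, and already summarises deviations by group; blood-draw dates are among the variables that SAP 4.9 requires. On that reading the Table 10 cell only describes the visit and nothing is lost. That is probably the intent, but the SAP does not say so, and the cell would still carry a window that differs from the protocol's.

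Calling this leftover text is an inference. The SAP's list of changes is not exhaustive: it also omits the move from Stata 17 to 18 and the change of sVNT units from percentage inhibition to U/ml. Version 1.0 of the SAP is not available. The half-extended cells of Table 10 make carry-over likely, but a deliberate narrowing cannot be ruled out.

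Months 18 to 30 do have windows in Protocol 7.1, and Month 30 is named in SAP Tables 8, 10 and 14 and in Section 9.4.1. Nobody would conclude that Month 30 goes unanalysed. This stands; the SAP gap there is one of completeness. Part of the count of 21 may also never materialise, because Protocol 4.9 says that assays beyond IgG and the 30-month visit depend on further funding.

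On SAEs, the Table 11 timepoint column, SAP Table 4, SAP 6.1.2 and Protocol 3.2.2 agree on 12 months. Protocol 8.2 could mean following recorded events to resolution, and the extension consent text in Protocol 4.9 names infections and blood samples, not SAEs. It may be that none were collected after Month 12. If so, the label is the error, and it still needs correcting. Protocol 7.1 remains in direct conflict with the 12-month wording.

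**Conclusion.** The concern holds, at minor severity. The SAP and the protocol give different Month-12 windows, 29 against 61 days, and the SAP does not say whether its own window restricts the data. The extension to Month 30 is incomplete in Table 10 and Section 4.8. The study-end SAE rows contradict their own timepoint in a study that can run to 30 months.

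The practical effect cannot be sized from the documents. The number of Month-12 samples drawn 15 to 30 days off target is unknown, and the effect on the analysis is nil if the outcome cell is only descriptive. The number of SAEs recorded after Month 12 is also unknown and may be zero. Only secondary immunological endpoints from Month 12 onward and two descriptive SAE rows are involved. The conclusion assumes that the protocol supplied is the Version 8.0 that the SAP cites.

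**What to change.** **Windows.** In SAP Table 2, set Visit 7 to ±30 days and add Visits 8 to 10. In SAP Table 10, extend the title, the variable, analysis-set and outcome cells and the footnote to Month 30, with Month 6 at ±14 days and Months 12, 18, 24 and 30 at ±30 days, as in Protocol 7.1. Add one sentence: samples are analysed at their nominal visit whatever the draw day, and the number outside the window is reported by group. An in-window sensitivity analysis is optional. Add a Month-30 trigger to SAP 4.8.

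**SAEs.** First establish whether SAEs were collected after Month 12. Then reconcile Protocol 1.3, 3.2.2, 7.1 and 8.2 with SAP 4.9, 6.1.2, Table 4, Table 11 rows ix and x, and Dummy Table S2. If they were collected, tabulate SAEs up to Month 12 and after Month 12 separately by arm, with the number still under follow-up in each period. If not, relabel the rows as SAEs to Month 12.

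**Cost.** A few table cells, one sentence on sample timing, one added trigger, reconciled SAE wording, and one check of what was collected. It is best done before the affected later-timepoint analyses.

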11.3.2. Secondary outcomes

Binding antibodies - changes from baseline will be expressed as geometric mean fold ratios (GMFR), calculated as the ratio of the post-booster GMC to the baseline GMC. GMCs will be compared between the two vaccine groups and between the vaccine and control groups at 6, 12, 18, 24 and 30 months. We will account for age in the analysis.

Functional antibodies seven time points for vaccine groups [baseline, 1, 6, 12, 18, 24 and 30 months] and six time points for controls [baseline, 6, 12, 18, 24 and 30 months] – for the C-PASS assay (sVNT), data are reported as percentage (%) inhibition by neutralising antibodies using the manufacturer’s instructions. A <30% inhibition is considered negative, while ≥30% inhibition is considered positive. Data will be presented as mean and standard deviation.

Neutralizing assay (20% subset of samples at all time points) up to 12 months – Data will be reported as endpoint titre calculated using the Reed/Muench method (23). A titre of 10 reflects undetectable neutralizing activity.

Cellular immunity: (on a 50% subset at seven time points for vaccine groups and six time points for controls)

Quantiferon COVID IFNy release assay up to 12 months – Levels of IFNy will be reported in IU/ml according to the manufacturer’s instructions. Data will be reported as GMT and 95% confidence intervals.

IFNy Elispot – The number of IFNy-producing cells/million PBMCs will be reported using means and 95% confidence intervals.

Intracellular cytokine staining – The data will be reported as the frequency (%) of cytokine-expressing T cells (e.g., total T cells, CD4 T cells, CD8 T cells). Cytokines such as IFNy (Th1) and IL-5 (Th2) will be measured as a minimum. This will be presented as means and 95% confidence intervals.

Multiplex cytokine assays – A 10-plex panel of cytokines will be measured in supernatants from the Elispot studies. Cytokine concentrations will be reported in pg/ml, and data will be presented as GMT and 95% confidence intervals.

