5 DESCRIPTIVE STATISTICS

5.1 PARTICIPANT DISPOSITION

A CONSORT flow diagram will be used to summarise the study population from screening to analysis, including the number of people who were:

- Screened for eligibility
 - and were eligible at screening
 - and were ineligible at screening (screen failures)*
- Eligible at screening but not randomised*
- Ineligible at screening but randomised (protocol violation)*
- Eligible and randomised (or not randomised for the control group)

[Subsequent numbers will be given by study group]

- Allocated to each study group
 - and received the allocated vaccine
 - and did not receive the allocated vaccine*
- Included in the Reactogenicity and Safety Population (according to vaccine received not allocated)[^]
- Included in the Primary Day-28 Immunology Population[^]
- Included in the Month-6 Immunology Population[^]
- Included in the Month-12 Immunology Population[^]

* Reasons will be provided.

[^]The number of participants with missing data will be noted. Missing data arising from lost-to-follow-up or withdrawal will be enumerated, including the level of withdrawal (from intervention, follow-up, or both, and consent to use data up to the time of withdrawal) and reasons (harms-related reasons for withdrawal will be emphasised).

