			Month-6	Group A vs B, Group A vs control, Group B vs control
			Month-12	Group A vs B, Group A vs control, Group B vs control
			Month-18	Group A vs B, Group A vs control, Group B vs control
			Month-24	Group A vs B, Group A vs control, Group B vs control
			Month-30	Group A vs B, Group A vs control, Group B vs control
Functional antibody sVNT (Omicron BA.1), U/ml	GM (95% CI)	GMR (95% CI)	Day-28	Group A vs B
			Month-6	Group A vs B, Group A vs control, Group B vs control
			Month-12	Group A vs B, Group A vs control, Group B vs control
			Month-18	Group A vs B, Group A vs control, Group B vs control
			Month-24	Group A vs B, Group A vs control, Group B vs control
			Month-30	Group A vs B, Group A vs control, Group B vs control
Functional antibody sVNT (Omicron BA.4/5), U/ml	GM (95% CI)	GMR (95% CI)	Day-28	Group A vs B
			Month-6	Group A vs B, Group A vs control, Group B vs control
			Month-12	Group A vs B, Group A vs control, Group B vs control
			Month-18	Group A vs B, Group A vs control, Group B vs control
			Month-24	Group A vs B, Group A vs control, Group B vs control
			Month-30	Group A vs B, Group A vs control, Group B vs control
Neutralising antibody				
Neutralising antibody (Wuhan), NT50	GM (95% CI)	GMR (95% CI)	Day-28	Group A vs B
			Month-6	Group A vs B, Group A vs control, Group B vs control
			Month-12	Group A vs B, Group A vs control, Group B vs control

Neutralising antibody (variant of concern) #, NT50	GM (95% CI)	GMR (95% CI)	Day-28	Group A vs B
			Month-6	Group A vs B, Group A vs control, Group B vs control
			Month-12	Group A vs B, Group A vs control, Group B vs control
Cellular mediated immunity				
Ag1 IFN γ (IU/ml)	GM (95% CI) or median (95% CI) [^]	GMR (95% CI) or difference in medians (95% CI) [^]	Day-28	Group A vs B
			Month-6	Group A vs B, Group A vs control, Group B vs control
			Month-12	Group A vs B, Group A vs control, Group B vs control
Ag2 IFN γ (IU/ml)	GM (95% CI) or median (95% CI) [^]	GMR (95% CI) (95% CI) [^]	Day-28	Group A vs B
			Month-6	Group A vs B, Group A vs control, Group B vs control
			Month-12	Group A vs B, Group A vs control, Group B vs control

GM: Geometric mean. GMR: Geometric mean ratio

#variants of concern for neutralising antibody to be confirmed

[^]Data will summarised using medians, and compared across groups using difference in medians in the case of negative and zero values and log-transformation not possible

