Dummy Table 2. Immune responses at <<Day-28/Month-6/Month-12/Month-18/Month-24/Month-30>> by study group and comparison across groups. Lines to be added for additional endpoints/timepoints.

	Moderna (N = n)	Novavax (N = n)	Control (N = n)	Moderna/ Novavax	Moderna/ Control	Novavax/ Control
Endpoint at timepoint x	GM (95% CI) [n=xx]	GM (95% CI) [n=xx]	GM (95% CI) [n=xx]	GMR (95% CI)	GMR (95% CI)	GMR (95% CI)
Endpoint at timepoint y	Median (95% CI) [n=xx]	Median (95% CI) [n=xx]	Median (95% CI) [n=xx]	Difference in medians (95% CI)	Difference in medians (95% CI)	Difference in medians (95% CI)

GM = geometric mean, GMR = geometric mean ratio

*There will be no comparisons with the control group at Day 28

Dummy Table 3. Breakthrough infections by study group.

[figure not shown]
	Moderna (N = n)	Novavax (N = n)	Control (N = n)	Total (N = n)
Received additional dose (Total)	N (%)	N (%)	N (%)	N (%)
Before Month-6 visit	N (%)	N (%)	N (%)	N (%)
Between 6 and 12 month visit	N (%)	N (%)	N (%)	N (%)
Between 12 and 18 month visit	N (%)	N (%)	N (%)	N (%)
Between 18 and 24 month visit	N (%)	N (%)	N (%)	N (%)
Between 24 and 30 month visit	N (%)	N (%)	N (%)	N (%)
Total breakthrough blood samples collected (% of BTI)	N (%)	N (%)	N (%)	N (%)
Total breakthrough blood samples collected (% of BTI)	N (%)	N (%)	N (%)	N (%)

*Table to be repeated for undocumented breakthrough infections

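### The 86 planned vaccine-versus-control comparisons have no estimand row of their own, and Table 10's randomised-arm model is a weak choice for a non-randomised control group under 60

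*SAP*

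**What the plan says.** For every outcome and visit after Day 28, SAP Table 8 (section 8.1) lists "Group A vs B, Group A vs control, Group B vs control". The block headed "Cellular mediated immunity" does so at Months 6 and 12 only. Dummy Table 2 has columns for both control comparisons, with the note "There will be no comparisons with the control group at Day 28". The disposition plan (SAP 5.1) also carries Group C through: "Eligible and randomised (or not randomised for the control group". Protocol 11.3.2 plans binding-antibody comparisons "between the vaccine and control groups at 6, 12, 18, 24 and 30 months. We will account for age in the analysis".

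Table 10 (SAP 8.1.1) is headed as generic for the later endpoints in Table 8. Its estimand compares the two vaccine groups, "irrespective of SARS-CoV-2 infection or receipt of a 5 th dose (self-initiated". Its analysis set is "All randomised participants as per randomisation with complete outcome and covariate data". Its model estimates a difference "between the vaccine arms, adjusted for the stratifying variable (age group), primary series and first booster vaccine", plus baseline level.

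Group C is not randomised and is recruited below age 60 (SAP 3.2). Groups A and B have no upper age limit (SAP 3.4). Controls may take a fourth dose and stay in follow-up (Protocol 7.2.1). The lead-in to SAP 6.5 treats receipt of any COVID-19 vaccine as an intercurrent event, but its event table and Tables 13 and 14 name only a fifth dose. Table 13 does so while listing the control arm, and its analysis set is again randomised participants only.

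**The concern.** A model that suffices between randomised arms has more to do when the comparison group is self-selected. Three features of Table 10 fit the control comparisons poorly.

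- **Age.** Adjustment is for under 50 versus 50 and over. The upper stratum mixes vaccinees of any age from 50 with controls aged 50-59, so part of the contrast has no overlap.
- **Baseline history.** Prior SARS-CoV-2 infection and time since third dose are absent. Both can be derived from Day 0 data in all three groups, and the Day-28 models already use time since first booster. Baseline level captures them only in part.
- **Extra doses.** A control who changes their mind receives a fourth dose, which the fifth-dose wording does not describe.

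The third feature bears on a stated question. One secondary objective asks whether a fourth dose adds immunological benefit over a third, judged by cellular immunity in Group C against A and B. With some controls dosed, a treatment-policy estimate compares vaccinating now with possibly vaccinating later. That is a legitimate estimand, but it is not four doses versus three, and the hypothetical-strategy analyses in Table 14 are written for A versus B only.

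**Working it through.** **1. The plan's own figure.** Inputs from SAP 3.5: coefficient of variation 1.15, ratio 1.4, 90% power, two-sided 0.05. Log SD s = sqrt(ln(1 + 1.15²)) = 0.918. Then n = 2(1.960 + 1.282)² × 0.918² / (ln 1.4)² gives 157 per arm, within 3% of the stated 160; 160/0.8 = 200. The same s is used below. It was set for Day-28 IgG, so carrying it to other outcomes and visits is an assumption.

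**2. Count of control comparisons in Table 8** (outcomes × visits × 2):
- binding antibody 4 × 5 × 2 = 40
- sVNT 3 × 5 × 2 = 30
- neutralising antibody 2 × 2 × 2 = 8
- IFN-γ 2 × 2 × 2 = 8

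The total is 86. Of these, 78 are fixed as geometric mean ratios; the 8 IFN-γ comparisons may become differences in medians.

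**3. Interval half-width factor** = exp(1.96 × s × sqrt(1/n1 + 1/n0)), before loss to follow-up:
- 225 vs 150: 1.21
- cellular-immunity subset, 112 vs 75 (75 + 37 per vaccine arm, Protocol summary of blood schedule): 1.31

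**4. Age.** Assumed, as the documents give no values: 40-60% of vaccinees aged 50 or more are 60 or more (f); 15-33% of controls are 50-59; the conditional ratio for 60+ versus 50-59 is 0.7-1.25 (t).
- Overall: the upper stratum's weight W, from n1·n0/(n1 + n0) in each stratum with 150 and 75 vaccinees, is 0.20-0.33. The factor exp(W·f·ln t) is 0.93-1.05.
- In a subgroup aged 50 and over: t^f runs from 0.7^0.6 = 0.81 to 1.25^0.6 = 1.14. The matching half-width, 75 vaccinees versus 22.5-49.5 controls (15-33% of 150), is 1.39-1.54.

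**5. Prior infection.** Assumed: prevalence differs by up to 20 points in either direction, with a residual ratio of up to 1.5 after baseline adjustment. 1.5^0.2 = 1.08 and 1.5^-0.2 = 0.92. If age and infection acted in the same direction, the extremes multiply to 0.932 × 0.922 = 0.86 and 1.045 × 1.084 = 1.13, still inside the half-width (1/1.21 = 0.83 to 1.21).

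**6. Dosed controls.** If a share x of controls takes a fourth dose, each then matches a vaccinee, and no vaccinee takes an extra dose, a ratio G reads G^(1-x). For G = 2.0 this is 1.74 at x = 20% and 1.52 at x = 40%. This is the distance between two estimands, not bias in the treatment-policy one. Extra doses among vaccinees would change it, and the formula does not apply to differences in medians.

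**The case against.** The strongest reply is that the plan covers most of this already. Table 10 is headed generic for Table 8, and its footnote says the endpoints are analysed alike. SAP 6.5 opens by counting any COVID-19 vaccine. SAP 4.9 locks extra-dose data, and Dummy Table S 1 tabulates uptake in controls. Where Tables 13 and 14 show a main-analysis strategy for a self-initiated dose, it is treatment policy, and with no rule discarding later values the controls' data would be used that way in practice. All of this stands. Relabelling the dose alone would be a wording change.

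It is also fair that the 78 antibody comparisons serve an objective worded as descriptive, that controls were recruited as not planning a fourth dose, that cellular-immunity comparisons end at Month 12 in Table 8 (which limits uptake), and that the model already adjusts for baseline level.

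A reader might infer that a control's extra dose has no assigned strategy anywhere. That cannot be shown: Table 10's intercurrent-event cells are not readable in the available text. The point rests on its estimand sentence, the 6.5 event table and Tables 13 and 14. A reader might also infer that Group C was forgotten; SAP 5.1 and Dummy Table 2 show otherwise. What the reply leaves open is the choice of method: nothing in it supplies an overlapping age range, the omitted baseline covariates, or an analysis aimed at four versus three doses.

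**Conclusion.** The concern holds as a choice of analysis for the control comparisons. Table 10 was built for randomised arms, and better methods for a non-randomised contrast are available at almost no cost in precision.

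The likely distortion is small overall: about 0.92-1.08 from age or prior infection taken singly, against a half-width of 1.21. In a subgroup aged 50 and over the age effect could reach 0.81-1.14, but that subgroup's own half-width is about 1.39-1.54, and SAP 9.5 merely does not exclude control comparisons from its age subgroups. These sizes rest on assumed age mix, infection prevalence and effect ratios. The documents do not support reading the control comparisons as invalid or seriously biased.

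The more substantive gap is narrow: the 8 cellular-immunity comparisons carry the fourth-versus-third-dose objective, and no planned analysis of them targets that question once controls are dosed. The primary endpoint and all A versus B analyses are unaffected.

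**What to change.** Add a row to Table 10 for A versus C and B versus C:

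1. **Analysis set:** all enrolled participants aged under 60 at Day 0 in Groups A, B and C.
2. **Adjustment:** continuous age, baseline level, prior SARS-CoV-2 infection by history reported at Day 0 (one definition), primary series, first booster vaccine and time since third dose.
3. **Extra doses:** define the event as any COVID-19 vaccine dose taken outside the study after Day 0. Keep treatment policy as the main estimate, read with the uptake in Dummy Table S 1. Add a hypothetical-strategy supplementary analysis for the 8 cellular-immunity control comparisons, applied alike in all three groups.
4. **Table 13:** correct the analysis set to include enrolled controls. Those endpoints are descriptive only.

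Leave the A versus B rows as they are. SAP 4.8 analyses each visit as it completes, so label the change post hoc for any visit already analysed.

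**Cost:** SAP wording, re-specified models using Day 0 data, and 8 imputed analyses. On the age mix assumed above, 30-45 of the 75 older vaccinees per arm drop out, leaving 180-195 versus 150: the half-width goes from 1.21 to about 1.22. In the cellular-immunity subset (90-97 versus 75) it goes from 1.31 to 1.32-1.33. The hypothetical analysis is wider: 1.34-1.35 at 20% control uptake (60 controls left) and 1.38-1.39 at 40% (45 left), if imputation recovers nothing and no vaccinee takes an extra dose. Control comparisons would then apply to adults under 60, the group for which Group C was recruited.
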